11.3 PK/PD Outcome Measures

11.3.1 PK Outcome Measures

- Plasma concentrations of PRN1008 at approximately the time of maximum concentration on Day 1 and at various subsequent times during outpatient dosing

11.3.2 PD Outcome Measures

- Percentage BTK occupancy for individuals in peripheral blood mononuclear cells (PBMCs) at 2 & 24 hours after the first PRN1008 dose and at varied subsequent times during outpatient dosing
- Change from baseline in anti-dsg1-3 autoantibody levels by ELISA at various time points

11.3.3 Exploratory PK/PD Analysis

Exploratory PK/PD analysis will examine the effects, if any, of covariates on PK and/or PD, and the relationship between PK, PD, and efficacy in this population.

11.4 Determination of Sample Size

Sample size for this pilot study was determined pragmatically by the number of subjects required to determine a preliminary safety profile and a point estimate for the primary endpoint of efficacy. If the clinical response rate is 50%, 25 subjects in each Part will result in an 80% CI of $\pm 13\%$. Results from this pilot study will be used to design confirmatory clinical trials.

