
Statistical Analysis:
	
Clinical Activity:
 
Given the natural history of PV to not remit spontaneously, a study of approximately 25 PV patients completing 12 weeks of treatment and approximately 25 PV patients completing 24 weeks of treatment with PRN1008 should determine a reasonable approximation of the responder rate and average time to response (e.g., estimated response rate of 50% with 80% CI of $\pm 13\%$). Where appropriate, patients from both parts will be combined in analysis. The results from this pilot study will be used to design confirmatory, pivotal clinical trials. Time course of changes in clinical and laboratory parameters will be described graphically, and at each visit using descriptive statistics.

	
Safety and Tolerability: Quantitative safety data will be summarized by descriptive statistics (arithmetic mean, standard deviation, median, minimum, and maximum) by dose level. Summaries will also be presented for the change from baseline, when appropriate.
 
Pharmacokinetics and Pharmacodynamics: Individual and group PK and PD data will be summarized, displayed graphically, and by descriptive statistics for each visit, where measured.

Study Duration:	Approximately 48 months from the first subject treated to last subject completing, and 28 (Part A) – 32 (Part B) weeks per subject.

GLOSSARY OF ABBREVIATIONS AND TERMS

ABBREVIATION OR TERM	DEFINITION
ABSIS	Autoimmune Bullous Skin Disorder Intensity Score
ABQOL	Autoimmune Bullous Diseases Quality of Life (assessment)
AE	Adverse event
Ae	Amount excreted unchanged in the urine
ALP	Alkaline phosphatase
ALT	Alanine aminotransferase
ANOVA	Analysis of variance
AST	Aspartate aminotransferase
AUC	Area under the plasma concentration-time curve
BCR	B-cell receptor
BID	Twice daily (morning and evening)
BMI	Body mass index
BP	Blood pressure
BPM	Beats per minute
BTK	Bruton's Tyrosine Kinase
CA	Competent Authority
CI	Confidence Interval
CLr	Renal clearance
Cmax	Maximum observed plasma concentration
CNS	Clinical Network Services
CPK	Creatine phosphokinase
CR	Clinical Response
CRF	Case report form
CRO	Contract research organization
CTCAE	Common Terminology Criteria for AEs
CV	Coefficient of Variation
CYP	Cytochrome P450
DBP	Diastolic blood pressure
DSG	Desmoglein
EC	Ethics Committee (see also HREC)
ECG	Electrocardiogram
EDC	Electronic Data Capture
ELISA	Enzyme-Linked Immunosorbent Assay
FSH	Follicle Stimulating Hormone
FDA	Food and Drug Administration

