3.4. Dose Adjustment/Modifications

Initial PRN1008 dosing will be 400 mg *bid*. Patients will return to the study center and complete the visit procedures per the Schedule of Assessment (Appendix 15.1). The investigator will review the patient's clinical response, tolerability, and BTK occupancy to determine if a dose-adjustment is needed (Appendix 15.2). The maximum dose in this study, after dose-adjustment, will be 600 mg *bid*. Doses may range from 100 mg *bid* to 600 mg *bid* in 100 mg *bid* increments (100 mg is the smallest tablet size). CS rescue treatment will be initiated, if indicated (Appendix 15.3).

“Well tolerated” is defined as the absence of Grade 3 or greater gastrointestinal AEs, or Grade 2 non-gastrointestinal AEs, including liver function changes, related to PRN1008 therapy. Investigators should use their judgment of the risk-benefit of continuing therapy by weighing the extent of clinical response, and AEs potentially related to PRN1008 therapy. In general, PRN1008 should be stopped and conventional therapy started when tolerability is poor and clinical response is also suboptimal.

4. General Statistical Considerations

Continuous data will be described using descriptive statistics (i.e. n, mean, standard deviation, median, minimum, and maximum). Categorical data will be described using the frequency and percentage in each category. For the summary statistics of all numerical variables unless otherwise specified, minimum and maximum will be displayed to the same level of precision as reported. Mean and median will be displayed to one level of precision greater than the data collected. Standard deviation / standard error will be displayed to two levels of precision greater than the data collected. P-values will be rounded to three decimal places. If a p-value is less than 0.001 it will be reported as “<0.001”. If a p-value is greater than 0.999 it will be reported as “>0.999”.

Due to the small sample sizes, all p-values derived from inferential analyses will be considered informative. In general, all significant testing will be two-sided at significance level 0.05. All tests will be made without adjustment for multiplicity or multiple comparisons. Two-sided 80% and 95% Confidence Intervals of the response rate for efficacy endpoints will be provided.

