4.1. Sample Size

Sample size for this pilot study was determined pragmatically by the number of patients required to determine a preliminary safety profile and a point estimate for the primary endpoint of efficacy. If the clinical response rate is 50%, 25 patients will result in an 80% CI of $\pm 13\%$. Results from this pilot study will be used to design confirmatory clinical trials. Sample size will be reevaluated based on an interim analysis when approximately 6 patients have completed 4 weeks of PRN1008 therapy.

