8.1. Primary Efficacy Endpoint

The primary efficacy endpoint is “The proportion of patients who are able to achieve CDA within 4 weeks of starting PRN1008 treatment without the need for doses of prednis(ol)one >0.5 mg/kg at any time”.

Other types of CS are converted to dose-equivalent prednis(ol)one (see Section 8.2.6).

This is operationalized as meaning the first CDA is achieved on or before the Week 5 visit but after first dose of PRN1008, and will be summarized, by maximum dose level to the Week 5 visit and overall in a table, using frequencies and percentages. In addition, two-sided 80% and 95% CIs (Confidence Intervals) of the response rate will be provided for each maximum dose level and overall using the Exact (Clopper-Pearson) method.

Patients who are able to achieve CDA between first dose of study drug and the Week 5 visit and have no occurrence of daily prednis(ol)one >0.5 mg/kg before the date of the first CDA will be considered as responders, even if the CDA status was not maintained or higher doses of prednis(ol)one were used after the first CDA. Patients who are not able to achieve CDA prior to or at the Week 5 visit or have any occurrence of daily prednis(ol)one >0.5 mg/kg before a first CDA during the study treatment will be considered as non-responders. Patients whose CDA status is unknown at the Week 5 visit for whatever reason (include early termination before Week 5 visit) will be also considered as non-responders. Only systemic CSs (as defined by medication taken orally or intravenously) are to be used to evaluate the efficacy endpoints, topical CSs will not be counted.

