5.4 Efficacy Analyses

The mITT population will be used for all efficacy analyses. For analyses at a particular study drug dose, all patients who received that dose at least once will be included. In addition, for selected analyses, where specified, the Completer and PP population will be used.

The descriptive statistics will be done by dose level and overall for all study visits, unless specified otherwise. All binomial confidence intervals for efficacy analyses will use the Exact (Clopper-Pearson) method. Patient data listings will be listed by starting dose, patient, dose level and study visit.

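### The stated 80% CI of ±13% at n=25 is a normal-approximation width; the exact interval both SAPs require gives about ±14.4 points

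*Protocol*

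**What the plan says.** Protocol 11.4 (Determination of Sample Size) gives one precision figure: "If the clinical response rate is 50%, 25 subjects in each Part will result in an 80% CI of" ±13%. Part A SAP 4.1 repeats it for Part A alone: "If the clinical response rate is 50%, 25 patients will result in an 80% CI of" ±13%. Part B SAP 2.3 repeats the protocol sentence. The synopsis, under Statistical Analysis, offers the same figure as an example, after saying that the planned numbers "should determine a reasonable approximation of the responder rate and average time to response". None of the four places names the interval method behind the figure.

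The method for the analysis is named in the SAPs. Part A SAP section 4 (General Statistical Considerations) says "Two-sided 80% and 95% Confidence Intervals of the response rate for efficacy endpoints will be provided". Part A SAP 8.1 says that the intervals for the primary endpoint "will be provided for each maximum dose level and overall using the Exact (Clopper-Pearson) method". Part B SAP 5.4 is general: "All binomial confidence intervals for efficacy analyses will use the Exact (Clopper-Pearson) method".

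On the basis for the number itself, protocol 11.4 says "Sample size for this pilot study was determined pragmatically by the number of subjects required to determine a preliminary safety profile". Its second stated aim is to estimate the primary efficacy rate. No target interval width is set.

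**The concern.** The planning sentence predicts the width of the 80% interval that 25 patients will produce, and each SAP prescribes a method that produces a wider one. The mismatch sits inside each SAP: Part A 4.1 against 8.1, and Part B 2.3 against 5.4. Since ±13% is the only precision figure offered for 25 patients per part, a reader who takes it at face value will expect a tighter interval than the report will contain.

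**Working it through.** **Inputs.** Response rate 50%, 25 patients per part and an 80% confidence level (protocol 11.4); two-sided intervals (Part A SAP section 4); Clopper-Pearson method (Part A SAP 8.1, Part B SAP 5.4).

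**Step 1: reproduce the stated figure.** The normal-approximation half-width is z × √(p(1−p)/n), with z = 1.2816 for a two-sided 80% interval:

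1.2816 × √(0.5 × 0.5 / 25) = 1.2816 × 0.10 = 0.128, or ±12.8 points, which rounds to ±13%.

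The plan's figure is reproduced.

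**Step 2: apply the planned method.** For x responders among n, the Clopper-Pearson 80% limits are the 10th percentile of Beta(x, n−x+1) and the 90th percentile of Beta(x+1, n−x). Exactly 50% cannot be observed with 25 patients, so the two nearest outcomes are used:

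| Responders | Observed rate | Exact 80% CI | Half-width |
|---|---|---|---|
| 12/25 | 48% | 33.8% to 62.5% | 14.4 points |
| 13/25 | 52% | 37.5% to 66.2% | 14.4 points |

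**Step 3: the gap.** 14.4 − 13 = 1.4 points against the stated figure (14.36 − 12.82 = 1.5 points against its unrounded value).

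**Step 4: is the gap only rounding?** If the true rate is 50%, the expected exact half-width over all possible outcomes with 25 patients is 14.1 points. The half-width is 13.5 points or less only if 7 or fewer, or 18 or more, of the 25 respond. That has probability 4.3%. For 13.0 points or less the probability is 1.5%. So the reported interval would seldom round to ±13%.

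**Step 5: other sizes.** Exact 80% half-widths at a rate of, or nearest to, 50%:

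| n | Half-width |
|---|---|
| 20 (assumed) | 16.2 points |
| 22 (assumed) | 15.4 points |
| 25 | 14.4 points |
| 30 | 13.03 points |
| 31 | 12.8 points |
| 50 (both parts combined) | 9.9 points |

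The sizes 20 and 22 are illustrations; the documents give no dropout rate. The 95% interval, also planned, has an exact half-width of 20.4 points at n=25, against 19.6 by the normal approximation.

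**The case against.** The strongest reply is that ±13% is not an error. It follows from the plan's own inputs by a standard formula, protocol 11.4 names no interval method, and the protocol never mentions Clopper-Pearson. Other approximate methods agree with it: at n=25 the Wilson half-width is 12.4 points and the Jeffreys half-width 12.5. Much of the excess reflects the conservatism of the exact method, whose actual coverage at a true rate of 50% and n=25 is 89.2% for a nominal 80% (the normal approximation covers 77.0%). All of this stands. It means that the defect is a mismatch between planning formula and analysis method, not wrong arithmetic.

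Three stronger readings are tempting, and the documents do not support them.

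- *That the trial misses its precision target.* There is none. The size was set pragmatically, and no decision rule depends on 13 points.
- *That the figure will mislead the confirmatory trials.* Protocol 11.4 and the synopsis say that the pilot's results will inform those trials, and the results will carry their own exact intervals.
- *That the Part B efficacy set will usually fall below 25.* Part B SAP 5.4 analyses efficacy in the mITT population, which requires treatment up to Week 5 and a Week 5 assessment (3.2.4), and Part B SAP 2.2 caps each part at 25, so a shortfall is possible. But the synopsis plans for about 25 patients completing each part, and protocol 11.8.2 allows replacement of patients who leave for non-safety reasons. The documents do not show that a shortfall is the usual case.

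What survives is that the same SAPs state one width and prescribe a method that gives another.

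**Conclusion.** The point holds as a minor inconsistency. At 25 patients and a response rate of about 50%, the planned exact 80% interval has a half-width of about 14.4 points, so the stated ±13% is about 1.4 points too favourable as a description of what will be reported. This rests on the 50% rate and 25 analysed patients that the plan itself assumes. The primary rate is also to be reported by dose level, where the numbers are smaller and the intervals wider still; the planning figure speaks only to the whole part. Neither the sample size nor any planned analysis is called into question.

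**What to change.** In the protocol synopsis, protocol 11.4, Part A SAP 4.1 and Part B SAP 2.3, replace ±13% with: *about ±14.4% (exact Clopper-Pearson 80% CI, n=25)*. If a width for a smaller evaluable number is added, label that number as an assumption, for example n=22, ±15.4%, or n=20, ±16.2%.

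The cost is one phrase in four places and a slightly less favourable stated figure. No extra patients are needed, and no analysis or trial procedure changes.

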11.5 Analysis Populations

Four study populations will be defined: Screening Population, Safety Population, Efficacy Population, and Pharmacokinetic Population.

11.5.1 Screening Population

All participants who provide informed consent and have screening assessments evaluated for study participation are included in the Screening Population.

11.5.2 Safety Analysis Population

All participants who have received at least one dose of PRN1008 will be included in the safety analysis. The Safety Analysis Population will be defined for all safety analyses.

11.5.3 Efficacy Analysis Population

All patients who have received at least one dose of PRN1008 will be included in the efficacy analysis. Subject response and disease progression will be determined using PDAI, ABSIS, ABQOL, and TABQOL scores. Efficacy data will be presented in listings by subject and tabulated for each efficacy endpoint. Data may be combined where appropriate for Parts A

and B. Additional sub-group analyses (e.g. disease severity, dose group) may be performed as appropriate.

11.5.4 Pharmacokinetic Analysis Population

A pharmacokinetic population will be defined for participants who provide adequate plasma concentration data to allow for PK analysis. Participants may be excluded from the PK population if they significantly violate the inclusion or exclusion criteria, deviate significantly from the protocol, or if data are unavailable or incomplete, all of which may influence the analysis. Excluded cases will be documented together with the reason for exclusion in the Clinical Study Report.

11.6 Randomization and Blinding Procedures

Not applicable; the study is open-label.

11.7 Subject Numbers and Treatment Assignments

As they are enrolled in the study, subjects will be assigned a unique consecutive number. The site, in conjunction with the Sponsor, will be responsible for assignment of all unique subject numbers and dose assignments.

11.8 Subject Disposition, Subject Replacement, and Demographics and Baseline Characteristics

11.8.1 Disposition

The numbers of subjects enrolled, completing, and withdrawing, along with reasons for withdrawal, will be tabulated. The number of subjects in each analysis population will be reported overall.

11.8.2 Replacement of Subjects

Participants prematurely discontinued from the study for non-safety reasons may be replaced at the discretion of the Sponsor, to ensure adequate numbers of evaluable participants. A patient is considered "evaluable" if they took one or more doses of the study drug. Each patient who provides informed consent will be assigned a unique subject identifier (USUBJID). Participants recruited to be replacement patients will be assigned the next available subject identifier.

11.8.3 Demographics and Baseline Characteristics

Demographic and baseline characteristics (pemphigus type, age, sex, race, ethnicity, weight, height, and body mass index) will be summarized for the Safety Population using descriptive statistics. No formal statistical analyses will be performed, and no inferential statistics reported.

Prior and concomitant medications will be summarized overall, by dose level, and by the number and percentage of subjects taking each medication, classified using World Health Organization Drug Dictionary Anatomical Therapeutic Chemical classes and preferred terms (WHODD).

Disposition, baseline demographics and subject characteristics will be summarized for the Safety Population.

11.9 Efficacy Analysis

11.9.1 Subject Response and Disease Progression

Subject response and disease progression will be determined using PDAI, ABSIS, ABQOL, and TABQOL scores. Efficacy data will be presented in listings, by subject, and tabulated overall. Data may be combined where appropriate for Parts A and B. Additional sub-group analyses (e.g. disease severity, dose group) may be performed as appropriate.

The PDAI, ABSIS, ABQOL, and TABQOL questionnaires are located in [Appendix 5](#).

11.10 Safety Analysis

Quantitative safety data will be summarized by descriptive statistics (arithmetic mean, standard deviation, median, minimum, and maximum) by dose level. Summaries will also be presented for the change from baseline, when appropriate. All safety analyses will be based on the Safety Analysis Population. As appropriate, listings, summary tables and graphs (individual plots and/or mean plots) by period will be provided to the Investigator and to the SMC for safety and tolerability assessment.

11.10.1 Adverse Events

The original verbatim AE terms recorded on the participant's case report form (CRF) by the Investigator will be standardized by the Local Sponsor by assigning preferred terms and system organ classes from the most recent available version of the Medical Dictionary for Drug Regulatory Affairs (MedDRA).

AEs will be described by individual listings and frequency tables by preferred terms and body system. The NCI CTCAE, version 4.0 will be used for grading AEs.

11.10.2 Clinical Laboratory Tests

All clinical laboratory data will be stored in the database in the units in which they were reported. Normal ranges for the local laboratory parameters must be provided to Principia/designee before the study starts. Participant listings and summary statistics at each assessment time, including change from baseline, will be presented using the International System of Units (SI units; *Système International d'Unités*). Laboratory data not reported in SI units will be converted to SI units before analysis.

Clinical laboratory results will be summarized descriptively for baseline and each time point. The numerical change from baseline to each time point will be computed. In addition, laboratory shift tables will be provided for all laboratory parameters where low/normal/high or abnormal/normal status can be ascertained for shift from baseline to each time point. Listings of individual laboratory parameters by visit with normal ranges and abnormality assessments will also be completed by subject.

Scatter plots of the baseline value (x-axis) and end of study (y-axis) will be completed for each continuous clinical laboratory parameter. In addition, individual and group mean laboratory values over time (i.e., by visit) will also be completed to evaluate changes and trends in laboratory safety. Reference ranges will be highlighted on the plots to identify laboratory assessment out of range. Other graphical displays may be created as appropriate.

11.10.3 Vital Signs

Vital signs data will be presented by individual listings. Systolic blood pressure values < 90 or > 140 mmHg and diastolic blood pressure values < 60 or > 80 mmHg will be flagged as outside the normal range. Resting heart rate < 40 or > 100 beats per minute will be flagged as abnormal. Descriptive statistics of values and changes from baseline (mean, median, standard deviation) will be reported for quantitative variables separately for each period. In addition, tabular and graphical summaries will be used, as appropriate.

11.10.4 Concomitant Medications

The original terms recorded on the participants' CRF by the Investigator for concomitant medications will be standardized by the Local Sponsor by assigning preferred terms from the WHODD (World Health Organization Drug Dictionary) drug terms dictionary for treatments or coded via generic name of the concomitant medication.

Concomitant medications will be presented in summary tables and listings.

11.11 Pharmacokinetics/Pharmacodynamics Analyses

Individual and group PK and PD data will be summarized, displayed graphically, and by descriptive statistics for each visit where measured. Data will be summarized by descriptive statistics and related to clinical responses for each patient and as a group. PD and PD data will be pooled with data from other studies, and analyzed and reported separately.

11.11.1 Missing PK/PD Values

The methodology of handling missing PK/PD values in the analysis will be determined.

11.12 Statistical and Analytical Methods

11.12.1 Descriptive Summaries and Inference

Descriptive summary statistics will be provided for the safety, PK, and PD variables. For continuous variables, these statistics will typically include the number of subjects, mean, standard deviation, median, minimum, and maximum. For categorical variables, these statistics will typically include the number and percentage of subjects in each category. Descriptive summaries will be completed by study part, cohort, and dose.

Due to the small sample sizes, all p-values derived from inferential analyses will be considered informative. In general, all significant testing will be two-sided at significance level 0.05. All tests will be made without adjustment for multiplicity or multiple comparisons.

